**October 18, 2017**

# **The Effectiveness of Intervention on Insulin Injection in Insulin-naive Patients With Type 2 Diabetes: Application of the Transtheoretical Model**

## **Introduction**

If not well controlled, diabetes can easily trigger various complications. Maintaining a glycosylated hemoglobin (HbA1c) level lower than 7% has been established as the standard for diabetes control. Insulin treatment has been regarded as an effective method, and treating diabetes with insulin early on is widely considered as an important principle for treating patients with type 2 diabetes mellitus (T2DM) in the US and Europe. However, many studies have shown that patients with T2DM are often reluctant to change from oral medication to insulin treatment. Research has also found that patients with T2DM whose glycemic control was poor delayed insulin treatment by 7 to 8 years. Therefore, it is necessary for healthcare professionals to establish a comprehensive intervention plan to help patients with poor glycemic control to initiate insulin injection early and adhere to the treatment. However, as far as is known, little research has been done on this topic in Taiwan.

According to the Transtheoretical Model (TTM) proposed by Prochaska and Diclemente, people will experience different stages of change before the actual behavioral change takes place. Ineffectiveness of intervention to instigate behavioral change is largely due to failure to take into account the stage of change in which individuals are. The TTM suggests that decisional balance, which reflects the relative difference between pros and cons, is important for influencing the stage of change. In order to achieve behavioral change, the perceived pros of changing must be strengthened to outweigh the cons. In addition, individual must be self-convinced that the behavioral change is important for themselves. Subsequently, the process for behavioral change can be provided to facilitate behavioral change in individuals. The theory of TTM has

been applied to change various problematic behaviors, but so far, it has yet been used to improve the behavior of insulin initiation in insulin-naïve patients with T2DM. Thus, this study aims to assess the effectiveness of an intervention for insulin injection initiation based on the TTM in insulin-naïve patients with T2DM.

## **Methods**

### **Study design**

The present study adopts quasi-experimental design. To avoid contamination between participants in two study arms, cluster sampling is used. Patients with T2DM of an endocrinology clinic in southern Taiwan are assigned to the intervention arm, whereas patients at another endocrinology clinic in southern Taiwan are placed in the control arm. Eligible patients that match the inclusion criteria are recommended by doctors to initiate insulin treatment after getting the consent forms from eligible participants. Research assistants will subsequently collect baseline data from eligible participants. Afterwards, the participants in the intervention arm will receive the intervention. For the control arm, the participants will receive regular patient education originally administered at the hospital. Data for the participants in both study arms will be collected by research assistants at baseline, 3 months, 6 months, and 12 months post-intervention. The main outcome variable is change in HbA1c levels, while the change in stage of change, in insulin injection adherence, in appraisal of insulin injection, in patient empowerment, in self-efficacy for insulin injection, in diabetes distress, in quality of life, in triglyceride(TG), in total cholesterol (TC), in high-density lipoprotein cholesterol(HDL-C), in low density lipoprotein cholesterol(LDL-C), in urine albumin creatinine ratio (UACR), in estimated glomerular filtration rate(GFR) are secondary outcome variables. The outcome

variables and collection time points are summarized in Table 1.

## **Samples**

The inclusion criteria of eligible participants are: (1) diagnosed with T2DM for at least half a year; (2) aged 20-70 years old; (3) controlling diabetes only through oral medication, without previous experience in insulin injection; (4) HbA1c  $\geq 8.5\%$  as measured more than twice in the most recent year. Exclusion criteria were: (1) unable to communicate with language; (2) incapable of self-administering insulin injection due to visual or muscular impairment. Eligible participants who have been assessed and considered suitable for changing to insulin treatment by doctor will be included in this study.

Sample size estimation was done according to previous literature. An estimation of 63 participants in each study arm was calculated through setting a middle effect size of 0.5 between the two study arms in HbA1c levels,  $\alpha$  of 0.05, and power of 0.8. Furthermore, an attrition rate of 20% was expected. Therefore, each study arm should include at least 76 participants.

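### The minimum of 76 per arm does not cover the plan's own 20% attrition: 63 / 0.8 gives 79, and 76 leaves about 61 per arm with power of about 0.78 to 0.79

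*Combined protocol and SAP*

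**What the plan says.** The whole calculation is in the Samples section. It takes a standardised difference in HbA1c as its target ("setting a middle effect size of 0.5 between the two study arms in HbA1c levels"), with alpha "of 0.05, and power of 0.8", and reports the result as follows: "An estimation of 63 participants in each study arm was calculated". It then makes the attrition allowance: "an attrition rate of 20% was expected. Therefore, each study arm should include at least 76 participants".

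The section does not print the formula used to inflate 63 to 76, and it does not say whether alpha is one-sided or two-sided. Nothing elsewhere in the document gives a different target or a different attrition rate.

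**The concern.** Only people who have been enrolled can be lost, so an attrition rate is naturally a share of those enrolled. To keep 63 after losing 20%, the requirement is divided by 0.8. Multiplying it by 1.2 takes 20% of the number meant to remain, which is a smaller allowance. The step from 63 to 76 looks like this second calculation.

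If so, a trial that enrols exactly its stated minimum and sees exactly its expected attrition falls short of the 63 per arm that its power statement rests on. The calculation concerns the main outcome, so a reader would take 0.80 as the power with 20% loss already allowed for, and it is not.

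**Working it through.** **Inputs, all from Samples.** Standardised difference d = 0.5; alpha = 0.05; power = 0.8; equal arms, implied by the same n in each; attrition 20%; enrolment of at least 76 per arm. Two-sided testing is assumed, because it reproduces the plan's 63 and a one-sided test would give 50.

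**Step 1: reproduce 63.** With the normal approximation for two means,

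n per arm = 2 x (1.96 + 0.8416)² / 0.5² = 62.79, rounded up to 63.

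This matches the plan. There is no slack in it beyond rounding.

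**Step 2: reproduce 76.**

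- Multiplying by (1 + 0.20): 63 x 1.2 = 75.6, rounded up to 76. This matches.
- Dividing by (1 − 0.20): 63 / 0.8 = 78.75, rounded up to 79. This does not match.

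**Step 3: what 76 delivers.**

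- Remaining per arm at 20% loss: 76 x 0.8 = 60.8, about 61.
- Attrition at which 63 remain: 1 − 63/76 = 17.1%.
- Remaining per arm from 79 at 20% loss: 79 x 0.8 = 63.2.
- Shortfall: 79 − 76 = 3 per arm, or 158 − 152 = 6 in total, and 6/158 = 3.8%.

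**Step 4: power at the retained number.** The normal approximation is power = Φ(d x √(n/2) − 1.96). For n = 60.8 this is Φ(0.5 x √30.4 − 1.96) = Φ(0.797) = 0.787. The t-test column uses the noncentral t distribution.

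| n per arm | Normal approximation | t-test |
|---|---|---|
| 60.8 | 0.787 | 0.781 |
| 61 | 0.789 | 0.782 |
| 63 | 0.801 | 0.795 |
| 64 | 0.807 | 0.801 |

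Compared like for like, the attrition slip costs 0.801 − 0.787 = 0.014 (normal) or 0.795 − 0.781 = 0.014 (t-test), about 1.4 points of power.

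**A separate, smaller matter.** The t-test figures are lower partly because 63 came from the normal approximation. The exact t-test requires 63.77, so 64 per arm, which becomes 64 / 0.8 = 80 after attrition. That half point or so of power is not caused by the attrition step.

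**The case against.** Several points can be made for the plan.

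- **The effect is small.** About 1.4 points of power is little beside the uncertainty in a conventional medium effect size. This is true, and it limits how much the point matters. It does not make 76 follow from 63 and 20%.
- **The figure is a floor.** The plan says "each study arm should include at least 76 participants", so recruiting 79 or more would comply. But a stated minimum should be enough under its own assumptions, and stopping at 76 also complies.
- **The planned model may recover the loss.** Data Analysis specifies a REML linear mixed model adjusted for demographics and baseline values, and Table 1 has HbA1c measured at baseline, 3, 6 and 12 months. Someone who leaves after month 3 or 6 still contributes, and adjustment reduces residual variance by roughly r², where r is the correlation between baseline and follow-up. Offsetting 60.8 against 62.79 needs r² = 1 − 60.8/62.79 = 0.032, or r of about 0.18; against the t-test requirement of 63.77, r is about 0.22. The documents give no value for r, so any gain is an assumption, though the threshold is low. This is the strongest argument and it softens the practical consequence. It does not rescue the calculation, because Samples works from a simple two-group effect size, adds an attrition allowance, and claims no credit for repeated measures or baseline adjustment.
- **The formula is inferred.** The multiplication by 1.2 is not printed, and the denominator of the attrition rate is not defined. That is fair, and 76 is best described as consistent with 63 x 1.2. The contradiction does not depend on how 76 was obtained: losing 20% of 76 leaves about 61.

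**Conclusion.** The concern holds. At the plan's own 20% attrition, 76 per arm leaves about 61 instead of 63, and power on the calculation's own terms is about 0.78 to 0.79 instead of 0.80. The minimum is 3 per arm too low, and the stated 76 protects against 17.1% attrition at most.

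This is a minor arithmetic error and not serious underpowering. It should still be corrected, because the sample size is a figure the trial relies on and the inconsistency shows as soon as 76 is multiplied by 0.8. The conclusion assumes a two-sided test, equal arms, attrition counted as a share of those enrolled, and no contribution from those lost, which is how the Samples section treats them.

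**What to change.** Amend the final sentences of Samples in one of two ways.

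1. Set the minimum at 79 per arm and show the step: 63 / (1 − 0.20) = 78.75, rounded up. This costs 6 more participants in total (158 against 152).
2. Keep 76 and state what it provides: about 61 per arm and power of about 0.78 to 0.79 at 20% attrition, or 63 per arm if attrition is no more than 17%. This needs no extra participants and remains possible if recruitment has finished. Its only cost is a slightly less favourable power figure.

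In either case, state that alpha is two-sided and print the inflation formula. If the sponsor prefers the exact t-test as the basis, the corresponding figures are 64 and 80 per arm, and the text should say which method was used.

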## **Measurements**

### Biomedical indicator measurement

The HbA1c levels, triglyceride(TG), total cholesterol (TC), high-density lipoprotein cholesterol (HDL-C), low density lipoprotein cholesterol(LDL-C), urine albumin creatinine ratio (UACR) will be collected through blood test. Estimated glomerular filtration rate(GFR) will be collected through urine test. Height and weight will be collected through body weight and height scales, and will be converted to body mass index (weight (kg)/ height(m) ).

### Self-reported questionnaire

The other outcome variables will be collected by self-report questionnaire. The questionnaire will include following contents.

### *Demographic data & disease characteristics*

Age, sex, educational level, duration of diabetes, duration of taking oral drug before insulin therapy will be collected at baseline. Insulin treatment regimen including type of insulin, dose, frequency of injection and blood sugar self-monitoring will be collected after participants receiving insulin injection.

*Stage of change for insulin injection.* A question of stages of change for insulin injection was developed. At baseline, the question was “If the doctor recommends that you initiate insulin treatment right now, what would be your opinion?” Three responses to this question included “never considered”, “under consideration and might start within the next 6 months”, and “likely to start immediately”, which respectively represented three early stages of change — precontemplation, contemplation, and preparation. At the 3, 6, and 12 months post-intervention, the question was “what’s the status of your insulin injection?” The responses were “taking insulin injection previously, but now is stop insulin injection and never consider to receive insulin injection again”, “taking insulin injection previously, but now is stop insulin injection, consider to start insulin injection again within next 6 months”, “still receive insulin injection but sometimes forget to inject” , “Continuously inject insulin but less than 6 months”, “Continuously injected insulin and more than 6 months”.

*Insulin injection adherence.* An 8-item Morisky Medication Adherence Scale was used to assess insulin injection adherence behaviors of participants. The total scores ranged from 7 to 11. The higher scores indicate, the better insulin injection adherence behaviors

*Appraisal of insulin injection.* A 13-item Decisional Balance for Insulin Injection scale was used in the study to assess the appraisal of insulin injection. The scale comprised subscales of positive and negative appraisal. Each item was rated from 1 (strongly

disagree) to 5 (strongly agree). Decisional balance for insulin injection was calculated by deducting the mean score of positive appraisal with that of negative appraisal. The higher score indicated the higher decisional balance for insulin injection.

*Empowerment perception.* A 13-item Chinese version of the Diabetes Empowerment Process Scale was used to assess the perceived level of empowerment by healthcare providers in participants. Each item was rated on a 5-point scale with scores ranging from 0 (strongly disagree) to 4 (strongly agree). The total score range from 13 to 65. A higher score indicated higher perceived patient empowerment.

*Self-efficacy for insulin injection.* A 4-item scale was used to assess self-efficacy for insulin injection in participants. Each item was rated on a scale from 0 to 4 with 0 indicating “no confidence”, 1 indicating “20-30% confidence”, 2 indicating “40-50% confidence”, 3 indicating “60-70% confidence”, 4 indicating “over 80% confidence”. A higher score represented higher confidence in performing insulin injection.

*Diabetes distress.* An 8-item Chinese version of the short-form Problem Areas in Diabetes Scale was used to assess the levels of diabetes distress in participants. The response of each item was rated from 0 (not a problem) to 4 (serious problem). The total score ranged from 8 to 32. A higher score represented severer diabetes distress.

*Quality of life.* A 15-item Diabetes-Specific Quality-of-Life Scale was used to assess the subjective appraisal of participants in their perceived degree to which their current health-related aspects in life were affected by emotional suffering, social functioning, adherence to treatment regimen, and diabetic-specific symptoms. Each item was rated from “very much” (0 point) to “not at all” (4 points). The total score ranged from 0 to 60. A higher score indicated better quality of life.

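### The follow-up stage-of-change item has no response that is true of a participant who has not started insulin, and no rule says how to code one

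*Combined protocol and SAP*

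**What the plan says.** The Introduction gives the aim as to "assess the effectiveness of an intervention for insulin injection initiation based on the TTM". Under Samples, participants must be "without previous experience in insulin injection". Under Study design, doctors recommend insulin after consent; starting it is not a condition of entry. The same section lists the secondary outcomes, "while the change in stage of change, in insulin injection adherence" among them. Whether insulin was initiated is not itself a named outcome.

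The stage item is described under Demographic data & disease characteristics. At baseline it has three responses, for precontemplation, contemplation ("under consideration and might start within the next 6 months") and preparation. At 3, 6 and 12 months it changes to five responses. Two describe people who injected and stopped; the first reads "taking insulin injection previously, but now is stop insulin injection and never consider to receive insulin injection again", and the second differs in that the person may restart within 6 months. The other three describe people now injecting: with lapses, continuously for under 6 months, and continuously for over 6 months.

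The same section says that details of the insulin regimen "will be collected after participants receiving insulin injection". Table 1 lists stage of change at all four time points.

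**The concern.** An insulin-naive participant who has still not started at a follow-up visit cannot truthfully choose any of the five responses. The three pre-initiation stages recorded at baseline have no counterpart later, so change in stage has no valid follow-up value for someone who stays in precontemplation or moves only to contemplation.

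The plan itself makes such participants foreseeable. A person who answers "under consideration and might start within the next 6 months" at baseline could keep to that timetable and still be a non-starter at 3 months. Table 2 gives individual strategies for precontemplation and contemplation. Table 3 gives group activities for precontemplation, held every two months according to the note under Figure 1.

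At stake is a secondary outcome that fails for the very people in whom the target behaviour did not occur. If the intervention changes initiation, the fault falls unequally on the two arms.

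**Working it through.** **Step 1: set the responses against a never-starter.**

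| Follow-up response | Requires | True of a never-starter? |
|---|---|---|
| Stopped, will not consider again | past use | no |
| Stopped, may restart within 6 months | past use | no |
| Injecting, sometimes forgets | current use | no |
| Injecting continuously, under 6 months | current use | no |
| Injecting continuously, over 6 months | current use | no |

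None of the 5 fits. No other or not-applicable option is described, and there is no map from the follow-up responses to stages.

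**Step 2: inputs for an illustration.** The plan gives no initiation or stopping rate, so it has no figure of its own to reproduce here. From Samples: "each study arm should include at least 76 participants". Assumed: initiation *p* in control v intervention of 90% v 95%, 70% v 85% and 50% v 70%, and a share *s* = 10% of starters stopping in both arms.

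**Step 3: formulas.**
- True current injecting = *p*(1 − *s*).
- Never-starters missing: injecting among those answering = *p*(1 − *s*)/*p* = 1 − *s*.
- Never-starters recorded as stopped: apparent stopped = *ps* + (1 − *p*); true stopped = *ps*.
- Never-starters per arm = 76(1 − *p*).

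For 70% v 85%: true injecting is 0.70 × 0.90 = 63.0% v 0.85 × 0.90 = 76.5%, a difference of 13.5 points. With never-starters missing, it is 63.0/70 = 90% v 76.5/85 = 90%, a difference of 0. With never-starters recorded as stopped, the stopped share is 7.0 + 30 = 37.0% v 8.5 + 15 = 23.5%.

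**Step 4: results (control v intervention).**

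| Assumed initiation | True injecting | Difference | Difference if missing | True stopped | Stopped as recorded | Never-starters of 76 |
|---|---|---|---|---|---|---|
| 90% v 95% | 81.0% v 85.5% | 4.5 | 0 | 9.0% v 9.5% | 19.0% v 14.5% | 7.6 v 3.8 |
| 70% v 85% | 63.0% v 76.5% | 13.5 | 0 | 7.0% v 8.5% | 37.0% v 23.5% | 22.8 v 11.4 |
| 50% v 70% | 45.0% v 63.0% | 18.0 | 0 | 5.0% v 7.0% | 55.0% v 37.0% | 38.0 v 22.8 |

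The zero follows from taking *s* equal in the arms: only starters are left in the denominator. With *s* = 5% or 20%, the true difference in the middle case is 15 × 0.95 = 14.3 or 15 × 0.80 = 12.0 points, and it again reads as 0. In the recorded-as-stopped case, current injecting is unchanged, because never-starters stay in the denominator as non-injectors. If initiation is equal in the arms and never-starters are handled alike, the between-arm comparison does not shift.

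**Step 5: how much a formal test of initiation could show.** With a two-sided 0.05 unpooled z-test and 76 per arm with status known for all, ignoring clinic clustering, power for the three cases is about 22%, 61% and 73%. In the first case there are only 7.6 + 3.8 = 11.4 never-starters in total. These counts are before the loss planned for in Samples ("an attrition rate of 20% was expected").

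**The case against.** A reader might infer that never-starters cannot be told apart from stoppers or from drop-outs anywhere in the data. The documents do not support that. Regimen details are recorded once insulin is received, and Table 1 lists disease characteristics at every visit, so a stopper should have a regimen record. A never-starter who attends should also have HbA1c, lipids, renal measures and appraisal at 3, 6 and 12 months, which a drop-out would not. What stands is narrower: the item has no valid response, a blank regimen record fits both never started and not recorded, and the plan does not say that the record is used to classify stage.

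A second tempting reading is that recording never-starters as stopped reverses the study's conclusion. In Step 4 the direction of the stopped share does reverse, but the true differences there are only 0.5, 1.5 and 2.0 points, they follow from assuming equal stopping rates, and a stopped rate is not a named outcome. Moreover, the two stopped responses run parallel to baseline precontemplation and contemplation. If they were mapped that way, which is an inference since no map is written, many never-starters would land in the right stage; only someone likely to start at once would have no place. The serious loss is in the missing-data branch.

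Third, never-starters may be few. Enrolled patients are judged suitable for insulin and advised to start, and usual care teaches injection and includes a telephone check after 3 days. This stands as a limit on size. Suitability in a doctor's judgement is not acceptance by the patient, however, and the Introduction itself describes reluctance and long delay.

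Last, Figure 1 could not be seen. It is titled as the intervention-arm flowchart, and the item's responses are set out in the text.

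**Conclusion.** The gap in the item is certain from its wording; its effect is not. It touches one secondary outcome, change in stage of change, and leaves the primary HbA1c analysis alone. Bias between arms needs two things that the documents do not settle: that initiation differs by arm, and how never-starters are in fact coded. If they are left missing, the initiation effect drops out of the stage comparison (4.5, 13.5 or 18.0 points reading as 0 under the assumed rates). If they are recorded as stopped, the comparison of current injecting is sound, but non-initiation and discontinuation cannot be separated within the item. The point should be fixed because initiation is the stated aim and the remedy is cheap.

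**What to change.** 1. Add not-started responses to the 3-, 6- and 12-month item that mirror the three baseline stages: not considering; may start within 6 months; likely to start immediately.
2. Write a map from every baseline and follow-up response, including the one for occasional forgetting, to one ordered stage variable, with a separate flag for never started v stopped.
3. Derive insulin initiated (yes/no) by the same rule in both arms from the stage item and the regimen record. Report it by arm as a descriptive secondary result, with unknowns shown. Do not classify from a source that only one arm has, such as the interveners' information system or the control arm's telephone check. An adjusted logistic model is optional and may be too sparse, as Step 5 shows.

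The cost is three response lines, a written map and a derived variable, with no new visit or procedure. The stage item and Data Analysis are partly written in the past tense. If visits are complete, the responses cannot be added, and what remains is to derive initiation from existing responses and records and use it to separate never-starters from stoppers. None of this removes the confounding from having one clinic per arm, which applies equally to any comparison of initiation.

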### **Intervention plan of the intervention arm**

The intervention plan contains three parts: (1) individual intervention; (2) insulin injection follow-up management; (3) motivational group activities. Different

intervention strategies are applied to patients according to their stages of change. In addition, a computerized information system will be applied to facilitate data management and recording by interveners. The strategies for individual intervention designed according to the stage of change and the corresponding process of change are shown in Table 2. Details of insulin injection follow-up management from preparation stage to maintenance stage are shown in Table 3. The motivational group activities from precontemplation stage to maintenance stage are shown in Table 4.

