### **Data Analysis**

The statistical software program SPSS 17.0 was used for data analysis. The Chi-squared test and independent t-test were used to compare differences in personal characteristics and outcome variables between the two groups before and after intervention. Paired t-tests were used to examine within-group differences at baseline, 3 months, 6 months, and 12 months post-intervention. A linear mixed-effect model that adjusted for the demographic data and baseline outcome variables was used to examine the changing amount of outcome variables from baseline to 3 months, to 6 months, and to 12 months post-intervention between the intervention and control arms. Participants were considered as a random effect. First-order autoregressive was used in the mixed-effect model analysis with the restricted maximum likelihood (REML) approach. A  $p$ -value  $< .05$  was considered statistically significant.

Table 1. Outcome measures and collection time points

Measures	Baseline	3 rd month	6 th month	12 th month
Demographic data & disease characteristics	✓	✓	✓	✓
Body mass index	✓	-	✓	✓
HbA1c	✓	✓	✓	✓
Lipids (TC, HDL-C, LDL-C, TG)	✓	✓	✓	✓
Renal function: UACR, GFR	✓	✓	✓	✓
Stage of change for insulin injection	✓	✓	✓	✓
Insulin injection adherence	-	✓	✓	✓
Appraisal of insulin injection	✓	✓	✓	✓
Empowerment	✓	-	✓	✓
Self-efficacy	-	✓	✓	✓
Diabetes distress	✓	-	✓	✓
Quality of life	✓	-	✓	✓

Table 2. Individual intervention plan

Stage of Change	Strategy	Process of Change
Precontemplation	
 
• Use examples in which good/bad glycemic control has a positive/negative impact on significant others to help patients reflect on their own HbA1c control
 
• Explain current health condition to patients through the changes in the curves of the their data
 
• Use UKPDS Risk Engine to predict the risk of cardiovascular disease and cerebrovascular event in the future 10 to 20 years in individual patients
 
	Consciousness raising

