	
think about the relationship between insulin injection, diet, and physical activity
 
 
• Provide patient education on blood-glucose self-monitoring and assessment on the ability to deal with hypoglycemia
 
• Ask patients to continuously keep a daily record of the dose, time, site of injection, administration of blood-glucose self-monitoring, and incidents of hypo/hyperglycemia in the “Health Guardian Pamphlet”
 
	
Action	
 
• Educate family members to provide support for patients
 
• Build an instant online interactive system with professionals to provide feedback to patients
 
	Helping relationship
	
 
• Encourage patients to adhere to the insulin injection plan
 
• Healthcare professionals conduct telephone interviews and schedule return visits for patients on a regular basis
 
• Instruct patients how to adjust their diet and exercise flexibly according to insulin injection so as to decrease the chance of termination caused by barriers
 
• Teach patients to adjust the dose of insulin according to the results of blood-glucose self-monitoring
 
	Reinforcement management
	
 
• Patients promise to set mid-term and long-term goals
 
	Self-liberation

---

[figure not shown]
Table 3. Motivational group activity

Stage of Change	Strategy	Process of Change
Precontemplation	
 
• Listen to fellow patients in the stages of action and maintenance share the benefits of insulin injection and the ways to overcome obstacles
 
• Try out insulin injection
 
• Use pictorial or multimedia materials to illustrate the relationship between insulin and blood-glucose
 
	Self-reevaluation
Preparation	
 
• Listen to fellow patients in the stages of action and maintenance share the benefits of insulin injection and the ways to overcome obstacles
 
• Try out insulin injection
 
• Use pictorial or multimedia materials to illustrate the relationship between insulin and blood-glucose
 
	Self-reevaluation
Action	
 
• Share experience in insulin injection and provide support and solution
 
• Build mutually supportive partnerships with fellow patients
 
	Reinforcement management

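### The follow-up stage-of-change item gives current injectors overlapping answers, one defined by missed doses and two by time on insulin, so the split between them cannot be read cleanly

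*Combined protocol and SAP*

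**What the plan says.** Stage of change is one of the secondary outcomes named under Study design, and it is collected by self-report. The paragraph on stage of change, under Demographic data & disease characteristics, describes one question at 3, 6 and 12 months with five responses. The first two are for people who have stopped. The other three are for people still injecting:

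- option 3: "still receive insulin injection but sometimes forget to inject"
- option 4: "Continuously inject insulin but less than 6 months"
- option 5: "Continuously injected insulin and more than 6 months"

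Stages are assigned only to the three baseline responses, "which respectively represented three early stages of change". No stage, order or numeric code is given for the five follow-up responses.

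Missed doses have their own instrument: "An 8-item Morisky Medication Adherence Scale was used to assess insulin injection adherence behaviors of participants". Table 1 schedules it at 3, 6 and 12 months.

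The two arms have different recording duties. The Preparation row of the individual intervention plan (Table 2) includes "Ask patients to continuously keep a daily record of the dose, time, site of injection". The same instruction appears in the Action row of the follow-up management table (captioned Table 4). Usual care of the control arm lists only the recording of self-monitored glucose.

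**The concern.** A single-choice question needs answers that exclude one another. Here option 3 asks about missed doses, while options 4 and 5 ask about time on insulin. Someone who has injected for ten months and occasionally forgets is described by option 3. If continuously means not having stopped, option 5 describes that person as well. If it means never missing a dose, only option 3 fits and the time on insulin is not recorded.

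Two things are at stake. First, a difference between arms in the split between option 3 and options 4–5 could reflect time on insulin, missed doses, or willingness to report missed doses, and the item cannot say which. The stage outcome also partly repeats the adherence outcome. Second, a daily injection record in one arm may change how readily missed doses are noticed or reported there, so the ambiguity need not cancel between arms.

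**Working it through.** **Which answers a current injector can truthfully give at month 12**

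| Participant | Continuously = has not stopped | Continuously = never misses |
|---|---|---|
| Over 6 months, never forgets | 5 | 5 |
| Over 6 months, sometimes forgets | 3 or 5 | 3 (duration lost) |
| Under 6 months, never forgets | 4 | 4 |
| Under 6 months, sometimes forgets | 3 or 4 | 3 (duration lost) |

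The protocol does not choose between the columns and has no rule for a participant who fits two answers.

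**When it matters.** Samples requires no previous insulin injection. More than 6 months on insulin is therefore impossible at month 3 and borderline at month 6, so the long-term case is mainly a month-12 one.

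**Whether duration can be rebuilt.** The insulin data listed after initiation are type, dose, frequency and self-monitoring, with no start date. Earlier visits help: an insulin-naive entrant who chose options 3–5 at months 3, 6 and 12 had begun by month 3, so at least 12 − 3 = 9 months have passed since the start. Later starters, and interruptions between visits, remain unresolved.

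**What is not affected.** Options 3–5 against options 1–2 still separates people on insulin from people who have stopped, whatever is reported about missed doses.

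**Illustrative size.** The plan states no figure on this point. The sample size taken from it is 63 per arm, which reproduces: 2 × (1.960 + 0.842)² / 0.5² = 62.8, rounded up to 63 (two-sided test assumed).

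The remaining inputs are assumptions, not figures from the documents. Both arms behave identically, 70% inject at month 12, a share *f* of injectors sometimes forget, and a share *r* of those choose option 3. The share choosing option 3 is then 0.70 × *f* × *r*.

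| *f* | *r* control | *r* intervention | Option 3, control | Option 3, intervention | Difference |
|---|---|---|---|---|---|
| 0.5 | 0.5 | 0.5 | 17.5% | 17.5% | 0 |
| 0.3 | 0.5 | 0.7 | 10.5% | 14.7% | 4.2 points |
| 0.5 | 0.5 | 0.8 | 17.5% | 28.0% | 10.5 points |
| 0.5 | 0.5 | 0.9 | 17.5% | 31.5% | 14.0 points |

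Options 4 and 5 together move by the same amount the other way. In the third row they are 70 − 17.5 = 52.5% in control and 70 − 28.0 = 42.0% in intervention. Exchanging the two reporting rates reverses the sign of every difference.

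In simulation with 63 per arm, a chi-squared test on all five options rejects in about 7%, 19% and 31% of trials for the last three rows, and about 5% with equal reporting. This further assumes that the 30% who have stopped split equally between options 1 and 2, and that options 4 and 5 split 25:75. Collapsing to three categories (stopped, forgets, continuous) gives about 9%, 26% and 41%. The rates thus depend on how the table is formed, which the plan does not say.

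**The case against.** The strongest reply is that this is one ambiguous response set among many secondary outcomes, and that the more serious consequences a reader might infer are not in the documents. Most of that stands.

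- **Ranking.** A reader might infer that a long-term injector who forgets is ranked below someone who began last week. List order and the named stages suggest it, but no follow-up mapping or code is written, and a chi-squared analysis would not use rank.
- **Direction of bias.** A reader might infer that the diary makes the intervention arm look worse. The documents do not establish this. The diary may reduce missed doses, and coached participants may under-report lapses. The follow-up management table lists the diary under Action but not Maintenance, so diary-keeping by long-term injectors at month 12 is itself an assumption.
- **Persistence.** A reader might infer that staying on insulin can no longer be measured. It can, from options 3–5 against 1–2, and duration is partly recoverable from earlier visits.
- **Tailoring.** A reader might infer that the faulty item decides each participant's strategy. The plan says strategies follow stage, but not that interveners use this questionnaire, which research assistants collect.
- **Construct.** Treating irregular injectors as not yet in Action may be deliberate, because the plan's Preparation rows already include people who inject. Defining stage by status and duration alone would therefore be a debatable change of outcome.
- **Reporting.** A separate question on missed doses is still self-reported, so a reporting difference between arms would persist there. It would no longer be mixed with duration.

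None of this removes the overlap between option 3 and options 4–5.

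**Conclusion.** The point holds as a measurement defect in a secondary outcome. The three answers open to a current injector are not mutually exclusive, and the split between option 3 and options 4–5 combines missed doses with time on insulin. It bears mainly on month 12 and leaves HbA1c and the on/off-insulin comparison untouched.

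A difference in reporting between arms is possible because the listed recording duties differ, but its direction and size are unknown. The range of about 4 to 14 percentage points rests wholly on assumed rates (70% injecting, 30–50% of injectors forgetting, 50% against 70–90% reporting) and on identical behaviour. It shows what the item could produce and does not estimate what it will produce.

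**What to change.** At each follow-up visit, ask every current injector two things: (a) whether the present course of injections has lasted under or over 6 months, whether or not doses are missed; and (b) separately, whether doses are sometimes missed. Derive the stage categories from the two answers by a written rule fixed before analysis. Report the arm comparison on status and duration alongside the five-category version, so that the plan's own construct is kept and its components can be seen.

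The cost is one reworded item, one yes/no question and a line of coding, with no new visit. If collection has begun, rewording would break comparability between visits. In that case apply the change only to later visits, or add the two questions as a supplement to the existing item.
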